- Subjects with prior treatment for PCa including BT, RT or hormone therapy.

c) Number of Subjects:

This is a 3+3 dose escalation design study to determine the MTD. This study will use 2 dose levels and 1-6 subjects at each dose level. The first subject enrolled at each dose level (60 and 75 Gy) will be monitored for the entire DLT window (3 months post EBRT completion) with subsequent subjects enrolled either at the same dose (if only 1 of the first 3 subsequent subjects at the given dose experiences DLT) or in the

[Type here]

Protocol Title:	A Phase I Single-Arm Open Label Dose-Escalation Study of CivaSheet with Radical Prostatectomy with or without Adjuvant External Beam Radiation Therapy in Patients with High Risk Prostate Cancer
Principal Investigator Name/Contact Info:	[name]/ [contact]/ [contact]
Primary Contact Name/Contact Info	[contact] [name]
Date Revised:	7/22/2022
Study Number:	GCO#1: 16-1314

next dose level if the preceding dose is deemed acceptable (i.e., < 33% DLT within 90 days post EBRT). If in the first subject, Grade 4-5 hematuria, fistula formation, proctitis or death occurs in the DLT window, the trial will be terminated. The total number of subjects for this single arm 3+3 trial design is therefore a minimum of 1 and a maximum of 12.

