The dose escalation design utilized for the present study will proceed as follows: The first subject will be enrolled at 60 Gy. Once the entire DLT window (i.e., 90 days post EBRT) is complete for this first subject, the next 2 subjects will be enrolled at 60 Gy. If in the first subject, grade 4 or higher hematuria, proctitis, fistula formation or death occurs in the DLT window, the trial will be terminated. If 2 of the first 3 subjects experience DLT at 60 Gy, the trial will be terminated. If 0 or 1 of the first 3 subjects enrolled at 60 Gy experience a DLT after the third subject's entire DLT window is complete, an additional three subjects will be enrolled at 60 Gy. If $\geq 33\%$ of subjects experience DLT at 60 Gy, the trial will be terminated. If after the sixth subject's DLT window is complete and < 33% of subjects experience DLT at 60 Gy, the first subject at 75 Gy will be enrolled. Once the entire DLT window (i.e., 90 days post EBRT) is complete for this first subject at 75 Gy, the next two subjects will be enrolled at 75 Gy. If in the first subject at 75 Gy, grade 4 or higher hematuria, fistula formation, proctitis or death occurs in the DLT window, 60 Gy will be considered the MTD and no additional subjects will be enrolled at 75 Gy. If 2 of the first 3 subjects experience DLT at 75 Gy, 60 Gy will be considered the MTD and no additional subjects will be enrolled at 75 Gy. If 1 or 0 of the first 3 subjects enrolled at 75 Gy experience a DLT after the third subject's entire DLT window is complete, an additional 3 subjects will be enrolled at 75 Gy. If $\geq 33\%$ of subjects experience DLT at 75 Gy, no additional subjects will be enrolled at 75 Gy and 60 Gy will be considered the MTD. If after the sixth subject's DLT window is complete and < 33% of subjects experience DLT at 75 Gy, 75 Gy will be considered the MTD.

The true risk of toxicity is expected to be in the range of 10-50%. The following table shows the corresponding probabilities of dose escalation.

True Risk of Toxicity	0.1	0.2	0.3	0.4	0.5
Probability of Escalation	0.96	0.87	0.69	0.50	0.31

[Type here]

Protocol Title:	A Phase I Single-Arm Open Label Dose-Escalation Study of CivaSheet with Radical Prostatectomy with or without Adjuvant External Beam Radiation Therapy in Patients with High Risk Prostate Cancer
Principal Investigator Name/Contact Info:	[name]/ [contact]/ [contact]
Primary Contact Name/Contact Info	[contact] [name]
Date Revised:	7/22/2022

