Study Number:	GCO#1: 16-1314

A minimum of 3 and a maximum of 6 subjects within a dose level must be observed for one cycle (90 day post EBRT completion) before accrual to the next higher dose level may begin.

Three patients within a dose level must be observed for one cycle (30 days post EBRT) before accrual to the next higher dose level may begin. The treatment for this study is RP + Civasheet implant + adjuvant EBRT for patients with high-risk or intermediate (non-clinically localized) prostate cancer with adverse pathologic features including seminal vesicle invasion, extra prostatic extension or a positive surgical margin. Since the clinical guidelines recommend adjuvant EBRT post RP only for patients with adverse pathologic features at RP, patients without these adverse pathologic features at RP will be replaced with additional patients at that dose level. Since however eligibility criteria is for high risk or non-clinically localized intermediate risk prostate cancer, the anticipated number of patients without these adverse pathologic features who will not receive adjuvant EBRT is 2 or less. While toxicities among these patients will be monitored according to the protocol, toxicities among these patients will not be used in determinations of the MTD. The MTD will only be determined for patients undergoing RP + Civasheet implant + adjuvant EBRT.

If a subject is withdrawn from the study prior to completing the entire cycle of therapy or prior to completing the entire DLT window without experiencing a DLT prior to withdrawal, an additional subject may be added to that dose level. Subjects missing doses due to a DLT will not be replaced since these subjects will be considered to have experienced a dose limiting toxicity.

d) Study Timelines:

The duration of an individual subject's participation in this study including follow-up is 5 years.

The expected duration for the investigators to complete this ranges between 1 month for a minimum of 1 subject and 44 months for a maximum of 12 subjects.

Table 1. Time and events table for those undergoing RP + Civasheet implant + adjuvant EBRT.

[Type here]

Effective Date: 10/18/2022

End Date: 10/17/2023

Protocol Title:	A Phase I Single-Arm Open Label Dose-Escalation Study of CivaSheet with Radical Prostatectomy with or without Adjuvant External Beam Radiation Therapy in Patients with High Risk Prostate Cancer									
Principal Investigator Name/Contact Info:	[name]/ [contact]/ [contact]									

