hematuria, proctitis, or fistula are not observed. If 2 additional subjects are enrolled at 60 Gy, we will review for DLTs after completion of the 90 day DLT window and enroll 3 additional subjects at 60 Gy if DLT has been observed in 1 subject, or enroll 1 subject at 75 Gy if no DLT were observed or terminate the trial if $\geq 33\%$ DLT were observed in all subjects. For the next group of subjects at 60 Gy, we will review DLT/toxicity after all three subjects have completed the 90 days DLT window after EBRT. After the first subject's DLT window is complete (90 days post-EBRT) at 75 Gy, we will make a decision to enroll additional subjects at 75 Gy only if Grade 4-5 hematuria, proctitis, or fistula are not observed. If 2 additional subjects are enrolled at 75 Gy, we will review for DLTs after completion of the 90 day DLT window and enroll 3 additional subjects at 75 Gy if DLT has been observed in 1 subject, or terminate the trial if $\geq 33\%$ DLT were observed among the first three subjects at 75 Gy. For the next group of three subjects at 75 Gy, we will review DLT/toxicity after all three subjects have completed the 90 days DLT window. We will additionally describe rates of complications and toxicity (i.e., acute and late overall, GU and GI) by grade and by dose once the 6 month follow-up period is complete for all subjects. Toxicities among those not receiving EBRT will not affect the MTD determination or the decision to enroll additional patients at the same dose or at a higher dose. The DMC will review data at least once annually.

If the DMC recommends termination of the study we will terminate the study. If in the first subject at any dose Grade 4-5 hematuria, proctitis or fistula occur, we will terminate the study. If $\geq 33\%$ of subjects experience DLT (i.e., Grade 3 hematuria, proctitis, urinary retention) within the first 90 days post EBRT, the trial will be closed.

The Clavien-dindo classification of surgical complications will be used to assess complications and the NCI-CTCAE v4.0 in addition to the RTOG acute and late morbidity scoring criteria will be used to grade adverse events and toxicity.

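### After 0 of 3 DLTs at 60 Gy the protocol gives two different next doses with no precedence, and its printed escalation table fits neither rule

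*Protocol*

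**What the plan says.** **Step-by-step algorithm (Protocol 3(c)).** It introduces itself with "The dose escalation design utilized for the present study will proceed as follows". At 60 Gy the clause "If 0 or 1 of the first 3 subjects enrolled at 60 Gy experience a DLT" leads to three more subjects at the same dose. Escalation waits until six have been observed: "DLT window is complete and < 33% of subjects experience DLT at 60 Gy, the first subject at 75 Gy will be enrolled". The 75 Gy step is parallel: "If 1 or 0 of the first 3 subjects enrolled at 75 Gy experience a DLT", expand to six. Two DLTs in the first three is a stop at either dose.

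**Safety-monitoring text (Protocol, before the Adverse Events heading).** At 60 Gy, one DLT in three leads to three more subjects at 60 Gy. With none, the instruction is "or enroll 1 subject at 75 Gy if no DLT were observed or terminate the trial" at ≥33%. At 75 Gy it reads "enroll 3 additional subjects at 75 Gy if DLT has been observed in 1 subject, or terminate the trial if" ≥33% is seen among the first three. It gives no action for 0/3 at 75 Gy.

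**Other 3(c) text.** The opening paragraph ties further enrolment at the same dose to a condition covering both levels: "if only 1 of the first 3 subsequent subjects at the given dose experiences DLT". After the table comes "A minimum of 3 and a maximum of 6 subjects within a dose level must be observed for one cycle" before escalation.

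**Stopping Rules (Protocol).** The trial closes at ≥33% DLT at any dose level, with no minimum number of subjects.

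**SAP, Primary Outcome.** It defines the MTD by thresholds written variously as > 33%, ≥33% and < 33%. It has no decision rule at three subjects.

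**Escalation table (3(c)).** At true risks 0.1/0.2/0.3/0.4/0.5 the printed probabilities of escalation are 0.96/0.87/0.69/0.50/0.31.

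**The concern.** The primary outcome is the MTD, and this algorithm is what produces it. After 0/3 at 60 Gy, one part of the protocol assigns the next subject 60 Gy and another assigns 75 Gy, as a permanent implant. Two teams following the approved text could act differently on the same data, and each could be charged with deviating from the other passage.

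The table is the plan's only quantified statement of how the design behaves. If it describes neither written rule, those who approve and monitor the trial are working from operating characteristics the trial will not have.

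**Working it through.** **Inputs.** The rules and the printed table above. Assumptions: DLTs are independent with equal risk p; the first-subject Grade 4-5 stop is ignored; escalation means moving from 60 to 75 Gy. Since 1/3 and 2/6 are both 33.3%, < 33% at six subjects means at most 1/6.

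**Building blocks for three subjects.** P0 = (1−p)³, P1 = 3p(1−p)², P2 = 3p²(1−p).

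| p | 0.1 | 0.2 | 0.3 | 0.4 | 0.5 |
|---|---|---|---|---|---|
| P0, probability of 0/3 | 0.729 | 0.512 | 0.343 | 0.216 | 0.125 |
| P1, probability of 1/3 | 0.243 | 0.384 | 0.441 | 0.432 | 0.375 |

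**Attempt to reproduce the printed table.**

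- A: algorithm as written (0/3 and 1/3 expand, at most 1/6 escalates) = P0(P0+P1) + P1·P0.
- B: monitoring rule (0/3 escalates, 1/3 expands, at most 1/6 escalates) = P0 + P1·P0.
- C: A with 2/6 also accepted = P0(P0+P1+P2) + P1(P0+P1).
- D: B with 2/6 also accepted = P0 + P1(P0+P1).

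| p | 0.1 | 0.2 | 0.3 | 0.4 | 0.5 |
|---|---|---|---|---|---|
| Printed | 0.96 | 0.87 | 0.69 | 0.50 | 0.31 |
| A | 0.886 | 0.655 | 0.420 | 0.233 | 0.109 |
| B | 0.906 | 0.709 | 0.494 | 0.309 | 0.172 |
| B − A | 0.020 | 0.053 | 0.074 | 0.076 | 0.062 |
| C | 0.964 | 0.852 | 0.679 | 0.482 | 0.297 |
| D | 0.965 | 0.856 | 0.689 | 0.496 | 0.313 |

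Example for A at p = 0.3: 0.343 × (0.343 + 0.441) + 0.441 × 0.343 = 0.269 + 0.151 = 0.420.

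Neither written rule reproduces the table. The largest gaps, both at p = 0.3, are 0.69 − 0.420 = 0.27 for A and 0.69 − 0.494 = 0.20 for B. With 2/6 accepted, C comes within 0.018 and D within 0.014. Rounded to two decimals, D agrees in three of five cells (0.69, 0.50, 0.31) and C in one (0.96).

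**What the extra three subjects do after 0/3.** Under A they show two or more DLTs, and so stop the trial, with probability 1 − P0 − P1 = 0.028, 0.104, 0.216, 0.352, 0.500.

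**Literal ≥33% at 1/3.** If one DLT in three stopped the trial, the term P1·P0 would be lost from A or B: 0.177, 0.197, 0.151, 0.093, 0.047. Rule A would fall to 0.709, 0.459, 0.269, 0.140, 0.062.

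**The case against.** **The 0/3 choice changes little on average.** This stands. The shift is 0.02 to 0.08, and the monitoring rule puts only one subject at 75 Gy, observed for the full 90-day window under a Grade 4-5 stop. It limits the size of the effect but does not tell the team which dose to implant next.

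**The text can be reconciled.** Not fully. The algorithm presents itself as the design, while the other passage is monitoring text. Against that, the opening paragraph's condition and the minimum of three both lean towards escalating at 0/3, although six subjects also satisfy that minimum. No sentence ranks them.

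**The table settles it.** A reader might infer from the closer fit of D that escalation at 0/3 was intended. That is evidence, but not proof: D still misses two cells, and both C and D need 2/6 to escalate, which the written condition excludes. It would be equally wrong to say that the table carries no information about intent.

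**The 1/3 clash is only wording.** Mostly right. A reader might infer that the trial really stops at one DLT in three, but the explicit 1-of-3 expansion in both places points the other way, and the algorithm's own ≥33% sentence follows the expansion and reads as a six-subject test. The clash remains in the Stopping Rules, which give no minimum number, and in the 75 Gy monitoring sentence, which names the first three.

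**One third may be shorthand.** If 33% stands for one third, the SAP's > 33% would not trip at 2/6, and the table would agree. The sponsor may have meant this, but the written numbers do not say it.

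**Conclusion.** The plan is wrong as written on two counts and should be corrected. First, the action after 0/3 at 60 Gy is contradictory with no precedence. At risk 0.1 or 0.2, 0/3 is the most likely three-subject result (0.73 or 0.51). Second, the printed table describes neither rule, overstating escalation by up to 0.27 or 0.20.

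The ≥33% wording at 1/3 is secondary. The losses of 0.05 to 0.20 apply only under a literal reading that overrides the explicit expansion.

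A reader might also infer that the more cautious algorithm must be the correct rule. The documents do not support that; choosing it would be a preference, and the choice belongs to the sponsor.

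Two further inconsistencies are clean-up only. After a first-subject Grade 4-5 event at 75 Gy, the algorithm and the SAP name 60 Gy as the MTD, while the monitoring text and Stopping Rules simply end the study and the opening paragraph of 3(c) does not limit its termination to 60 Gy. Because 75 Gy is the top dose and the SAP already supplies the MTD, little turns on this. Section 3(c) also has a 30-day observation sentence beside the 90-day window.

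All figures rest on the assumptions listed in the working. They are escalation probabilities; MTD-selection probabilities were not computed.

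**What to change.** Choose one rule for 0/3 and state it in counts in Protocol 3(c), the monitoring text, the Stopping Rules and the SAP.

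- **Option 1, expand at 0/3.** Change the monitoring text's 0/3 action at 60 Gy, make the opening condition in 3(c) read 0 or 1 of the first three, and raise the minimum before escalation to six. The average cost at 60 Gy is 3·P0 more subjects: 2.2, 1.5 or 1.0 at risks 0.1, 0.2 or 0.3. After 0/3 it adds (42 + 35 + 90)/7 = 23.9, or about 24, weeks plus accrual.
- **Option 2, escalate at 0/3.** Amend the algorithm instead, keep the minimum of three, and say what 0/3 at 75 Gy does.

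Under either option 1/3 expands, 2 or more of 3 stops, at most 1/6 is acceptable, and 2/6 stops, as the literal thresholds say. Replace the ≥33% wording with these counts. The 12-subject ceiling is kept.

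Restate the table as 0.89/0.66/0.42/0.23/0.11 (option 1) or 0.91/0.71/0.49/0.31/0.17 (option 2), noting that it ignores the first-subject stop. If the sponsor intends 2/6 to be acceptable, change the < 33% and ≥33% thresholds and print 0.96/0.85/0.68/0.48/0.30 (option 1) or 0.97/0.86/0.69/0.50/0.31 (option 2).

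Clean-up: for a first-subject Grade 4-5 event at 75 Gy, say everywhere that 60 Gy is the MTD, with one event list that includes death and proctitis (the SAP omits death and in one place says prostatitis). Delete the 30-day sentence. Apart from option 1's extra subjects and time, the cost is a wording amendment to both documents.

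### The printed escalation probabilities (0.96 to 0.31) do not follow from either of the two escalation schedules the protocol writes, and those schedules disagree after 0 DLTs in 3 at 60 Gy

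*Protocol*

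**What the plan says.** Section 3(c) of the protocol (Number of Subjects) sets the schedule at 60 Gy. Two DLTs in the first three end the trial. The cohort grows to six under this condition: "If 0 or 1 of the first 3 subjects enrolled at 60 Gy experience a DLT". After the sixth subject, a rate of 33% or more ends the trial; otherwise "and < 33% of subjects experience DLT at 60 Gy, the first subject at 75 Gy will be enrolled". The section then expects a true toxicity risk of 10 to 50% and adds "The following table shows the corresponding probabilities of dose escalation": 0.96, 0.87, 0.69, 0.50 and 0.31 at risks 0.1, 0.2, 0.3, 0.4 and 0.5.

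The safety-monitoring text that precedes the Adverse Events section has another schedule at 60 Gy. One DLT in three adds three subjects at that dose, but with none the instruction is to "enroll 1 subject at 75 Gy if no DLT were observed".

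Other sentences in section 3(c) are compatible with that second schedule. The opening paragraph keeps the same dose "if only 1 of the first 3 subsequent subjects at the given dose experiences DLT". Further on, "A minimum of 3 and a maximum of 6 subjects within a dose level must be observed for one cycle", with 90 days after EBRT as the cycle. The next paragraph says "Three patients within a dose level must be observed for one cycle (30 days post EBRT", so the observation window also differs between adjacent paragraphs.

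At 75 Gy, one sentence of the safety-monitoring text adds three subjects if a DLT is "observed in 1 subject, or terminate the trial if $\geq 33\%$ DLT were observed among the first three subjects at 75 Gy". Under Adverse Events, Stopping Rules, the trial closes at 33% or more at any dose level. The SAP (Primary Outcome) moves the MTD down a level above 33%, accepts 75 Gy below 33%, and closes the trial at 33% or more at 60 Gy.

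**The concern.** The table is the only statement in either document of how the design performs. If it does not follow from the written rule, readers are misinformed about how often the trial reaches 75 Gy, or else the stopping text is stricter than the authors intended. One of the two must change.

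The two schedules also differ in conduct. After 0/3 at 60 Gy, section 3(c) treats three more men at 60 Gy, while the safety-monitoring text opens 75 Gy. At true risks of 0.1 and 0.2, 0/3 is the single most likely result.

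A smaller defect calls for the same edit. One DLT in the first three is 33.3%, so at 75 Gy it meets both the expand clause and the terminate clause of one sentence. The Stopping Rules conflict in the same way with section 3(c)'s expansion after 1/3.

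**Working it through.** **Inputs.** Cohorts of three; true DLT risk p = 0.1 to 0.5, with q = 1 − p (range from section 3(c)). Two or more DLTs in the first three stop the dose. The final threshold is below 33%. Since 1/6 = 16.7% passes and 2/6 = 33.3% fails, at most 1 DLT in 6 permits escalation. The first-subject stop for grade 4–5 events is left out because its rate is not given; it can only lower escalation.

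**Formulas.** P(0/3) = q³; P(1/3) = 3pq²; P(≤1/3) = q³ + 3pq².

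- A, section 3(c) as written: P(0/3)·P(≤1/3) + P(1/3)·P(0/3), which equals P(X ≤ 1 of 6).
- B, safety-monitoring text as written: P(0/3) + P(1/3)·P(0/3).
- C, schedule B with 2/6 accepted: P(0/3) + P(1/3)·P(≤1/3).
- D, schedule A with 2/6 accepted: P(0/3)·(1 − p³) + P(1/3)·P(≤1/3).

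**Example at p = 0.2.** q³ = 0.512, 3pq² = 0.384, P(≤1/3) = 0.896.

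- A = 0.512 × 0.896 + 0.384 × 0.512 = 0.655
- B = 0.512 + 0.384 × 0.512 = 0.709
- C = 0.512 + 0.384 × 0.896 = 0.856
- D = 0.512 × 0.992 + 0.384 × 0.896 = 0.852
- Printed: 0.87

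**Attempt to reproduce the table.**

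| True risk | 0.1 | 0.2 | 0.3 | 0.4 | 0.5 |
|---|---|---|---|---|---|
| Printed | 0.96 | 0.87 | 0.69 | 0.50 | 0.31 |
| A | 0.886 | 0.655 | 0.420 | 0.233 | 0.109 |
| Printed − A | 0.074 | 0.215 | 0.270 | 0.267 | 0.201 |
| B | 0.906 | 0.709 | 0.494 | 0.309 | 0.172 |
| Printed − B | 0.054 | 0.161 | 0.196 | 0.191 | 0.138 |
| C | 0.965 | 0.856 | 0.689 | 0.496 | 0.313 |
| D | 0.964 | 0.852 | 0.679 | 0.482 | 0.297 |

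No printed entry comes within 0.05 of A or B. C comes within 0.014 and D within 0.018, though neither is exact. Other readings fail too:

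- If 1/3 stops the dose and 0/3 escalates: 0.729, 0.512, 0.343, 0.216, 0.125.
- If 1/3 stops the dose and 0/3 expands: 0.709, 0.459, 0.269, 0.140, 0.063.
- At most 1 in 3 with no second cohort: 0.972, 0.896, 0.784, 0.648, 0.500.
- At most 2 in 6 with no look at three: 0.984, 0.901, 0.744, 0.544, 0.344.

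**What it means for the trial.**

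| True risk | 0.1 | 0.2 | 0.3 | 0.4 | 0.5 |
|---|---|---|---|---|---|
| Closure at 60 Gy, 1 − printed | 0.04 | 0.13 | 0.31 | 0.50 | 0.69 |
| Closure, 1 − A | 0.114 | 0.345 | 0.580 | 0.767 | 0.891 |
| Closure, 1 − B | 0.094 | 0.291 | 0.506 | 0.691 | 0.828 |
| P(0/3), where the schedules part | 0.729 | 0.512 | 0.343 | 0.216 | 0.125 |
| P(1/3), where the clauses overlap | 0.243 | 0.384 | 0.441 | 0.432 | 0.375 |
| Expected n at 60 Gy, A = 3 + 3·P(≤1/3) | 5.92 | 5.69 | 5.35 | 4.94 | 4.50 |
| Expected n at 60 Gy, B = 3 + 3·P(1/3) | 3.73 | 4.15 | 4.32 | 4.30 | 4.13 |

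**Effect of the first-subject stop.** P(escalation and a DLT in the first subject) is pq⁵ under both A and B. If 10 to 25% of DLTs were grade 4–5 (an assumption), escalation falls by at most 0.25 × 0.2 × 0.8⁵ = 0.016 at the five risks. That widens the gap.

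**The case against.** The arithmetic is hard to dispute; the objections concern weight and reading.

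- **The boundary, not the schedule, drives the gap.** This is correct. With 2/6 accepted, both schedules lie within 0.02 of the table; with 2/6 rejected, they differ from each other by only about 0.02 to 0.08. The mismatch remains, because the text rejects 2/6.
- **The table governs nothing.** No enrolment, stopping or MTD rule refers to it, and the text is the stricter of the two. That stands and limits the harm: following the text adds no toxicity. It does not answer the contradiction after 0/3, which does govern conduct.
- **33% may be shorthand for one third.** The SAP's wording of more than 33% could then admit 2/6, while its wording of less than 33% would not, leaving 75 Gy undecided at 2/6. This does not rescue the table, which describes the step up from 60 Gy: there section 3(c) and the SAP both close the trial at 33% or more.
- **The 1/3 overlap is a matter of tidying.** Largely fair. The explicit counts were probably meant to prevail, but neither document says so. P(1/3) shows how often the clauses overlap, not how often conduct would go wrong.

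**Conclusion.** The concern holds. The printed probabilities exceed those of the section 3(c) schedule by 0.07 to 0.27 and those of the safety-monitoring schedule by 0.05 to 0.20. At a true risk of 0.2, closure at 60 Gy has probability 0.34 or 0.29, against 0.13 implied by the table. Separately, the two schedules give opposite instructions after 0/3 at 60 Gy, an outcome with probability 0.73 at risk 0.1 and 0.51 at risk 0.2.

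This rests on independent DLTs with a common risk among evaluable subjects, on 2/6 counting as 33.3%, and on ignoring the first-subject stop, so the recomputed values are slight upper bounds. How the table was built is not stated. Acceptance of 2/6 is the closest match found, not an established explanation.

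**What to change.** Replace the 33% wording with one rule in DLT counts among evaluable subjects, stated identically in section 3(c), the safety-monitoring text, the Stopping Rules and the SAP's Primary Outcome.

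**Option 1 (default, because it is the design section's schedule).** At each dose, 2 or more DLTs in the first 3 stop that dose; 0 or 1 in 3 expands to 6; 0 or 1 in 6 is acceptable; 2 or more in 6 is not (at 60 Gy the trial closes; at 75 Gy the MTD is 60 Gy). Then:
- delete the immediate move to 75 Gy after 0/3 from the safety-monitoring text, and make its sentences for both doses expand after 0 or 1 in 3;
- change the opening paragraph of section 3(c) to 0 or 1 of the first 3, dropping the word subsequent;
- require six subjects, observed for 90 days, in both sentences on observation before escalation;
- print 0.89, 0.66, 0.42, 0.23, 0.11.

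**Option 2.** At 60 Gy, 0/3 escalates at once and 1/3 expands to 6; the rest is as above. Change section 3(c)'s 0/3 instruction at 60 Gy, but keep its expansion after 0 or 1 in 3 at 75 Gy, where the safety-monitoring text is silent on 0/3. Use 90 days throughout. Acknowledge that 60 Gy could then be named the MTD on three subjects. Print 0.91, 0.71, 0.49, 0.31, 0.17.

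**If 2/6 is meant to be acceptable,** change the text instead and print 0.96, 0.85, 0.68, 0.48, 0.30 (0/3 expands) or 0.97, 0.86, 0.69, 0.50, 0.31 (0/3 escalates at once).

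In every case, state that 1 DLT in the first 3 expands the cohort and does not trigger the stop. Add a footnote saying that the table ignores the first-subject grade 4–5 stop. The cost is wording in two documents and one table. The maximum stays at 12 evaluable subjects and no procedures are added.

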A Phase I Single-Arm Open Label Dose-Escalation Study of CivaSheet With Radical Prostatectomy With or Without Adjuvant External Beam Radiation Therapy in Patients With High Risk Prostate Cancer

[name]

NCT03657108

Document Date: 10-18-2022

**Primary Outcome:** We will determine the MTD for Civasheet when administered with RP and adjuvant EBRT. MTD is defined as the highest dose of the Civasheet® not yielding unacceptable toxicity. Specifically if > 33 % of subjects experience DLT at any dose level, the dose level below that level will be considered the MTD. Or if the highest level (75 Gy) has been reached and < 33% of subjects have experienced DLT, 75 Gy will be considered the MTD.. The present study defines dose limiting toxicity as the development of Grade 3 or higher (According to the NCI'S CTCAE v 4.0) urinary retention, hematuria or rectal bleeding/radiation proctitis within 90 days post EBRT which is given 6 weeks after RP + Civasheet implant for 5 weeks. Toxicities experienced among those not receiving adjuvant EBRT will not be used in the determination of the MTD. Binary or categorical outcomes will be described with proportion and 95% confidence intervals and continuous measures will be summarized with mean (SD) or median (IQR), as appropriate.

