While all genitourinary and gastrointestinal toxicities according to the NCI-CTCAE will be documented and evaluated every time a subject is seen Grade 3-5 hematuria, urinary retention and rectal bleeding/radiation proctitis are the specific toxicities used for dose escalation procedures. This study defines DLT as the development of NCI-CTCAE Grade >3 urinary retention, Grade 3 hematuria or Grade 3 rectal bleeding/radiation proctitis within 90 days post EBRT which is given 6 weeks after RP + Civasheet implant for 5 weeks. Grade 3 hematuria according to the NCI-CTCAE is defined as gross hematuria with indications including transfusion, IV medications, hospitalization, elective endoscopic, radiologic or operative intervention and limiting self-care activities for daily living. Grade 3 urinary retention is defined as an incomplete ability to empty the bladder with indications including elective operation or radiologic intervention, substantial loss of affected kidney function or development of mass. Grade 3 rectal bleeding/proctitis is defined as severe symptoms; fecal urgency or stool incontinence and limiting self-care activities for daily living. If > 33% of subjects experience these DLT at any dose, the dose level below that level will be considered the MTD. If  $\geq 33\%$  subjects experience a DLT at 60 Gy, the trial will be closed and no additional subjects will be enrolled. Also, if the first subject enrolled at 60 Gy experiences NCI-CTCAE Grade 4 or higher hematuria, fistula formation or proctitis, no additional subjects will be enrolled and the trial will be closed. If the first subject enrolled at 75 Gy experiences Grade 4 or higher hematuria, fistula formation or proctitis, no additional subjects will be enrolled at 75 Gy and 60 Gy will be considered the MTD. Grade 4 hematuria is defined as hematuria with life-threatening consequences and urgent radiologic or operative intervention indicated. Grade 4 or higher fistula (anal or urinary) formation is defined as a fistula with life-threatening consequences with urgent radiologic or operative intervention indicated. Grade 4 or higher proctitis is defined as proctitis with life-threatening consequences and urgent intervention indicated. The time frame for DLT evaluation is the first 90 days after EBRT. EBRT is given 6 weeks after RP+ Civasheet implant at 45 Gy in 25 fractions (Monday-Friday for 5 weeks). If > 33 % of subjects experience DLT at any dose level, the dose level below that level will be

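### The printed escalation probabilities follow from neither written escalation schedule and exceed both, by 7 to 27 points and by 5 to 20 points

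*Protocol*

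**What the plan says.** Protocol section 3(c), Number of Subjects, announces its only operating characteristics with "The following table shows the corresponding probabilities of dose escalation" and prints one row, "Probability of Escalation 0.96 0.87 0.69 0.50 0.31", for true risks of 0.1, 0.2, 0.3, 0.4 and 0.5. It names no rule or formula behind the row.

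Two escalation schedules are written out.

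- **Section 3(c).** Two DLTs in the first three subjects end the trial. "If 0 or 1 of the first 3 subjects enrolled at 60 Gy experience a DLT", three more subjects are enrolled at 60 Gy. After the sixth subject's window, if "< 33% of subjects experience DLT at 60 Gy, the first subject at 75 Gy will be enrolled". At 33% or more the trial ends.
- **Safety-monitoring text** (the DLT review steps ahead of the Adverse Events heading). After three subjects, three more are added if one had a DLT, "or enroll 1 subject at 75 Gy if no DLT were observed or terminate the trial" if the DLT rate is 33% or more. So 0 of 3 escalates at once.

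The threshold is worded in three ways. Section 3(c) opens with movement to the "next dose level if the preceding dose is deemed acceptable (i.e., < 33% DLT within 90 days post EBRT"). The Protocol's stopping rules close the trial at 33% or more. The SAP's Primary Outcome sets the MTD one level down "Specifically if > 33 % of subjects experience DLT at any dose level", yet also says that if 33% or more "subjects experience a DLT at 60 Gy, the trial will be closed and no additional subjects will be enrolled".

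**The concern.** With three or six subjects per level the possible DLT rates are few, and whether 2 of 6 passes decides most of the escalation probability. Two of six is 33.3%, which is not below 33% and does meet a stop at 33% or more. Under either schedule, six subjects at 60 Gy can then have at most one DLT if 75 Gy is to open. The printed probabilities look too high for so strict a rule.

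An IRB, a monitoring committee or a reader who judges the design by this row would misjudge it in both directions. At low risk the trial appears more likely to reach 75 Gy than the text allows. At high risk it appears less protective than the text makes it. The mismatch also raises the question of which rule the authors had in mind for 2 of 6.

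**Working it through.** **Inputs.** The risks p = 0.1 to 0.5 and the printed row come from section 3(c); the decision rules are those set out above. DLTs are taken as independent with constant risk p. The base case leaves out the first-subject Grade 4 or higher stop. It also follows the explicit instruction in both schedules to expand after 1 of 3, although 1 of 3 is itself 33.3%.

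**Formulas**, with P(k/3) the binomial probability of k DLTs in three subjects:

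- A, section 3(c) as written: P(0/3)·P(≤1/3) + P(1/3)·P(0/3), which equals (1−p)^6 + 6p(1−p)^5.
- B, safety-monitoring text as written: P(0/3) + P(1/3)·P(0/3). This text gives no separate limit for the second three subjects; the limit of 1 in 6 follows from its own closure at 33% or more.
- C, schedule B but accepting 2 of 6: P(0/3) + P(1/3)·P(≤1/3).
- D, schedule A but accepting 2 of 6: P(0/3)·P(≤2/3) + P(1/3)·P(≤1/3).

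**Worked case, p = 0.2.** P(0/3) = 0.512, P(1/3) = 0.384, P(≤1/3) = 0.896, P(≤2/3) = 0.992.

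- A = 0.512 × 0.896 + 0.384 × 0.512 = 0.6554
- B = 0.512 + 0.384 × 0.512 = 0.7086
- C = 0.512 + 0.384 × 0.896 = 0.8561
- D = 0.512 × 0.992 + 0.384 × 0.896 = 0.8520

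| True DLT risk | 0.1 | 0.2 | 0.3 | 0.4 | 0.5 |
|---|---|---|---|---|---|
| Printed | 0.96 | 0.87 | 0.69 | 0.50 | 0.31 |
| A | 0.8857 | 0.6554 | 0.4202 | 0.2333 | 0.1094 |
| Printed − A, points | 7.4 | 21.5 | 27.0 | 26.7 | 20.1 |
| B | 0.9061 | 0.7086 | 0.4943 | 0.3093 | 0.1719 |
| Printed − B, points | 5.4 | 16.1 | 19.6 | 19.1 | 13.8 |
| C | 0.9652 | 0.8561 | 0.6887 | 0.4959 | 0.3125 |
| D | 0.9645 | 0.8520 | 0.6795 | 0.4821 | 0.2969 |

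**Can the printed row be reproduced?** Not from A or B. C comes within 1.4 points everywhere and D within 1.8, so a rule that tolerates 2 of 6 is the likely source. That is an inference, since neither matches all five entries to two decimals: C rounds to 0.97, 0.86, 0.69, 0.50, 0.31 and D to 0.96, 0.85, 0.68, 0.48, 0.30. Two other readings fit less well. At most 1 DLT in 4 (one subject plus three subsequent subjects) misses by up to 5.1 points, and a single cohort of six accepting 2 misses by up to 5.4.

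**Sensitivity.** Applying the 33% stop literally at three subjects, so that 1 of 3 also ends escalation, widens the gap:

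- Schedule A becomes P(0/3)·P(≤1/3) = 0.709, 0.459, 0.269, 0.140, 0.063, a gap of 25 to 42 points.
- Schedule B becomes P(0/3) = 0.729, 0.512, 0.343, 0.216, 0.125, a gap of 19 to 36 points.

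The first-subject stop can only lower escalation. If every first-subject DLT triggered it, the term p(1−p)^5 would be lost. A would then be 0.83, 0.59, 0.37, 0.20, 0.09 and B would be 0.85, 0.64, 0.44, 0.28, 0.16.

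**The case against.** The strongest reply is that the table may be sound and the threshold wording loose. The row sits within 1.4 points of a 3+3 that accepts 2 of 6, and if 33% is shorthand for one third, the SAP's strict inequality would let 2 of 6 through. On this view, calling the table overstated presumes that the text is right.

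Part of this stands. The defect is a disagreement between table and text, and the overstatement is measured against the text without settling which should change. But the reply does not rescue the table as printed. Two of six is not below 33% however 33% is read, so section 3(c) excludes it. The SAP also closes the trial at 33% or more at 60 Gy, the level that governs escalation.

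Three smaller points are fair. The 1-in-6 limit in schedule B is derived from the closing rule, not stated for the second three subjects. The base case lets 1 of 3 pass while 2 of 6 fails, although both are 33.3%; it does so because the text expressly expands after one DLT, and it is the reading kinder to the printed row. The first-subject figures illustrate the direction of the effect and are not a bound: fistula triggers that stop without being a listed DLT, while urinary retention is a DLT that does not trigger it.

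It is also true that no enrolment decision, interval or MTD determination uses the row, and that the maximum of 12 subjects comes from the cohort rules.

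**Conclusion.** The point holds. The printed row is a stated property of the design that neither written schedule has. It exceeds section 3(c) by 7 to 27 points (ratio 1.08 at p = 0.1, rising to 2.83 at p = 0.5) and the safety-monitoring text by 5 to 20 points (ratio 1.06 to 1.80). At a true risk of 20% the table implies a 13% chance of not reaching 75 Gy, against 34% or 29% under the written rules. At 50% risk it shows escalation in 31% of trials, against 11% or 17%.

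These figures rest on independent DLTs with constant risk and on the reading most favourable to the printed row at three subjects. The other readings of the written schedules examined widen the gap. Because conduct follows the text, this should be fixed as a misdescription of the design; it is not an error that changes enrolment.

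**What to change.** 1. Reconcile the two schedules, which differ on what follows 0 of 3. Section 3(c) also says elsewhere that a minimum of 3 and a maximum of 6 subjects are observed before the next level opens, which bears on the same question.
2. Reconcile the wordings below 33%, 33% or more, and above 33% across Protocol section 3(c), the safety-monitoring text, the Stopping Rules and the SAP's Primary Outcome. State the limits as counts, covering both 1 of 3 and 2 of 6, so that rounding of one third cannot matter.
3. Recompute the row for the rule that is kept and print that rule, with the independence assumption, beside the table. If section 3(c) stands unchanged the row is 0.89, 0.66, 0.42, 0.23, 0.11. If the safety-monitoring schedule stands unchanged it is 0.91, 0.71, 0.49, 0.31, 0.17. Any other threshold needs its own calculation.

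Which rule should govern is for the sponsor and investigators to decide. The cost is wording in both documents and five recomputed numbers. If either written schedule stands, the stated chance of reaching 75 Gy becomes less favourable.
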